Subjects will be from 2 clinical subgroups, collectively designated as EAD for the purposes of this protocol: (a) MCI due to AD – intermediate likelihood and (b) mild Alzheimer's disease dementia. At study entry, subjects will be stratified according to clinical subgroup, *APOE* status (*APOE4* positive and negative), and the presence or absence of ongoing AD treatment with AChEIs or memantine or both. Randomization into the 2 clinical subgroups (see [Inclusion Criteria, Section 9.3.1 of the protocol](#)) is to remain reasonably balanced whereby at least 60% of the total number of subjects will have MCI due to AD – intermediate likelihood clinical subgroup and at least 30% will have mild Alzheimer's disease dementia. The subjects will be randomized into 1 of 6 treatment groups ([Table 1](#)) as explained in [Section 9.4.4](#) and [Section 9.4.5 of the protocol](#). *APOE4* status (positive or negative) must be confirmed for all subjects prior to randomization. After Protocol Amendment 05 based on the request from the Voluntary Harmonisation Procedure (VHP) committee, subjects who are confirmed *APOE4* positive (*APOE4* hetero- or homozygous) will not be randomized to the 10 mg/kg, biweekly dose. Randomization in the Core Study will initially be fixed to each of these dose groups (4:2:2:2:2:2 ratio, placebo to each of the 5 active treatment arms). All study personnel and subjects will be blinded with respect to the dose regimens. After 196 subjects have been randomized into the study, an interim analysis (IA) will be conducted and RAR will guide subsequent randomization into dose groups. Interim analyses and RAR will be repeated after 250 subjects have been randomized and again after each additional 50 subjects until all 800 subjects are randomized, and will then be conducted at 3-month intervals until all subjects complete 12 months of

treatment. A Bayesian analysis will be conducted at 12 months of treatment to assess for early success, and at 18 months of treatment, regardless of whether early success is achieved at 12 months.

Table 1 BAN2401 Dose Regimens

Study Arm	BAN2401 Dose (mg/kg)	Infusion frequency
1	Placebo	Biweekly ^a
2	2.5	Biweekly ^a
3	5.0	Biweekly ^a
4	10.0 ^b	Biweekly ^a
5	5.0	4-week intervals ^c
6	10.0	4-week intervals ^c

a: Biweekly = 2-week intervals

b: Subjects who are confirmed *APOE4* positive (*APOE4* hetero-or homozygous) will not be randomized to the 10 mg/kg, biweekly dose.

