5.4.4 Secondary Efficacy Analyses

The Full Analysis Set will be used in secondary efficacy analyses.

Key Secondary Endpoint Analyses

Key Secondary endpoints and corresponding analyses are ordered to reflect the most recent FDA draft guidance (February, 2018) and EMA Final Guideline (February, 2018) that prioritize effects on pathophysiology in early AD, as measured by biomarkers. Conventional analysis will be performed using all available data at the time of success (if applicable), and at 18 months of treatment, regardless of success. As described in section 5.4.1.2, conventional analysis will be based on the MMRM model including baseline as covariate, with treatment group, visit, randomization stratification variables (i.e., clinical subgroup [MCI due to AD, Mild Alzheimer's Disease Dementia], the presence or absence of ongoing AD treatment [AChEIs or memantine or both], *APOE4* status [positive, negative]), region, treatment group-by-visit interaction as fixed effects. If there is an imbalance across treatment groups based on randomization stratification variables, additional MMRM model will be run without the randomization stratification variables. In addition, ANCOVA model will also be used with treatment as a factor and baseline value as a covariate. These statistical models will be used to compare the combined 10 mg dose group (including bi-weekly and monthly regimens) with placebo for the key secondary endpoints. The rationale for combining the two 10 mg dose regimens is to account for the loss of subjects positive for *APOE4* in the 10 mg/kg biweekly dose group and the inability to randomize *APOE4* carriers to the 10 mg/kg biweekly group following a regulatory request by European Health Authorities in July 2014.

In addition, analysis will be performed for the following treatment comparisons:

- Combining 2 high doses (10 mg bi-weekly + 10 mg monthly), 2 middle doses (5 mg bi-weekly + 5 mg monthly), and the 2.5 mg bi-weekly dose, resulting in 3 treatment comparisons with placebo (for dose response)
- ED₉₀ dose of BAN2401 versus placebo, where the ED₉₀ dose of BAN2401 will be established by Bayesian analysis at 18 months as described in the next paragraph
- By treatment regimen (10 mg bi-weekly, 10 mg monthly, 5 mg bi-weekly, 5 mg monthly, 2.5 mg bi-weekly, placebo)
- Combining the top 3 doses (10 mg bi-weekly, 10 mg monthly, and 5 mg bi-weekly) versus placebo

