5.6.1 Extent of Exposure

Extent of exposure to study drug will be summarized as cumulative extent of exposure from Day 1 to Week 6 initially, and at 3 months increments thereafter. The cumulative number and percent of subjects will be presented by treatment group. Duration of exposure will be summarized using descriptive statistics and by duration categories; Day 1 to 6 weeks, 6 weeks to 3 months, and 3-month intervals thereafter. The number and percent of subjects will be presented by each duration category and treatment group. Overall exposure (number of subject-months) is defined as summation over all subjects' exposure durations and will be summarized by treatment group.

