5.6.2 Adverse Events

The AE verbatim descriptions (investigator terms from the CRF) will be classified into standardized medical terminology using the Medical Dictionary for Regulatory Activities (MedDRA). Adverse events will be coded to the MedDRA (Version 15.0 or higher) lower level term (LLT) closest to the verbatim term. The linked MedDRA preferred term (PT) and primary system organ class (SOC) will also be captured in the database.

A treatment-emergent AE (TEAE) is defined as an AE that emerged during treatment or within 90 days following the last dose of study drug, having been absent at pretreatment (Baseline) or

- Reemerged during treatment, having been present at pretreatment (Baseline) but stopped before treatment, or
- Worsened in severity during treatment relative to the pretreatment state, when the AE was continuous.

TEAEs and AEs will be followed for the entire duration of the study. Only those AEs that are treatment emergent will be included in summary tables. All AEs, treatment emergent or otherwise, will be presented in subject data listings.

Treatment-emergent AEs (TEAEs) will be summarized by treatment group on the Safety Analysis Set. The incidence of TEAEs will be reported as the number (percentage) of subjects with TEAEs by SOC and PT. A subject will be counted only once within a SOC and PT, even if the subject experienced more than one TEAE within a specific SOC and PT. The number (percentage) of subjects with TEAEs will also be summarized by maximum severity (mild, moderate, or severe). The number (percentage) of subjects with TEAEs will also be summarized by relationship to study drug (possibly related, probably related, and not related). TEAEs of special interest will be summarized similarly.

Adverse events will be summarized by the following subgroups: age (≤ 65 years, $65 < \text{age} < 80$, ≥ 80 years), sex (male, female), race (white, black, Asian, other), region, clinical subgroup (MCI due to AD – intermediate likelihood and mild Alzheimer's disease dementia), presence or absence of ongoing AD treatment (i.e., AChEIs and/or memantine), and *APOE $\epsilon 4$ carrier status* (positive, negative).

The number (percentage) of subjects with TEAEs leading to death will be summarized by MedDRA SOC and PT for each treatment group. A subject data listing of all AEs leading to death will be provided.

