6.3 ADAPTIVE RANDOMIZATION

Subjects will receive 18 months of treatment. Randomization to placebo or one of five dose arms of BAN2401 will be fixed for the first 196 subjects randomized in the study (4:2:2:2:2:2; placebo to each of the five active arms). Randomization probabilities to each arm will be updated at each IA such that the randomization probability will be increased for the placebo arm and arms that represent the potential target dose (ED_{90}), and simultaneously decreased for other active arms. At the time of Amendment 05 of protocol, the sponsor has agreed to the request from the Voluntary Harmonisation Procedure (VHP) committee that subjects who are confirmed *APOE4* positive (*APOE4* hetero- or homozygous) not be randomized to the 10 mg/kg, biweekly dose. After each interim analysis after protocol Amendment 05, the randomization probability vector will be split between *APOE4+* and *APOE4-* strata to ensure no subjects are enrolled on the 10 mg/kg biweekly dose. The overall probabilities as suggested by RAR will still be preserved. Details on the derivation of the adaptive randomization probabilities, are found in the Simulation Plan, see [Appendix 13.2](#).

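### TEAEs are summarised only as crude percentages of subjects, which can understate risk where observed time is short, possibly among APOE4 carriers on 10 mg/kg biweekly

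*SAP*

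**What the plan says.** Section 5.6.2 of the SAP fixes the measure: "The incidence of TEAEs will be reported as the number (percentage) of subjects with TEAEs by SOC and PT". It adds that "TEAEs of special interest will be summarized similarly". Deaths, SAEs and TEAEs leading to discontinuation are also given as number and percentage of subjects by SOC and PT. Only treatment-emergent events enter the summary tables, and such an event is "an AE that emerged during treatment or within 90 days following the last dose of study drug" (with further clauses for re-emergence and worsening). AEs are also tabulated by APOE4 carrier status.

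Section 5.6.1 states: "Overall exposure (number of subject-months) is defined as summation over all subjects' exposure durations and will be summarized by treatment group". Nothing in section 5.6 uses those subject-months as a denominator for AEs, and section 5.6.8 plans no other safety analyses.

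On follow-up, section 6.3 says "Subjects will receive 18 months of treatment", with no exception by arm. Section 3.2 says that after Protocol Amendment 05 confirmed APOE4 carriers "will not be randomized to the 10 mg/kg, biweekly dose". Section 5.4.4, when it explains why the two 10 mg/kg regimens are pooled for efficacy, names two things: "loss of subjects positive for *APOE4* in the 10 mg/kg biweekly dose group and the inability to randomize *APOE4* carriers" to the biweekly group.

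**The concern.** A percentage of subjects with an event is comparable between groups only if they were observed for similar lengths of time, or if events occur so early that later time adds nothing. Here observation for the TEAE tables ends with each subject's own dosing plus 90 days. Section 5.4.4 separates a loss of carriers from the bar on randomising new ones. The natural reading of the first is that some enrolled carriers left the 10 mg/kg biweekly arm before 18 months.

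Safety and tolerability by dose and regimen is primary objective 2 (section 3.1.1), and the AE table by arm and APOE4 status includes the group that the regulatory request concerned. SAP version 4.0 changed the efficacy comparisons to account for the missing carriers, but its revision table lists no corresponding change to the AE analyses. If carriers in that cell were observed for less time, their crude percentage could sit below that of fully followed groups for reasons unrelated to the drug, and a dose trend could be blurred.

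**Working it through.** **The plan's own figures.** The SAP states no expected AE rate. Its follow-up figures are dropout assumptions. Appendix 13.2, section 6.0, gives exponential dropout of 40% at 52 weeks and 22% at 26 weeks. Check: 1 − 0.60^(26/52) = 22.5%, consistent. These figures, and the 20% and 30% alternatives, are not specific to an arm, so they show no difference between arms.

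**Inputs for the illustration.**
- From the SAP: 18 months of planned treatment, and a TEAE window of 90 days after last dose.
- Assumed, because the SAP gives none: a full-follow-up risk R of 10%, 20% or 30%; a stop at 6, 9 or 12 months; a constant hazard.

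**Time at risk.** 90 days = 90/30.4375 = 2.96 months. Full follow-up is 18 + 2.96 = 20.96 months. Stopping at 6, 9 or 12 months gives 8.96, 11.96 or 14.96 months.

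**Formula.** Hazard h = −ln(1 − R)/20.96. Crude risk for a subject at risk for t months = 1 − exp(−h·t). For R = 20%, h = 0.2231/20.96 = 0.01065 per month, and at a 6-month stop the crude risk is 1 − exp(−0.01065 × 8.96) = 9.1%.

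| Full-follow-up risk | Stop at 6 months | Stop at 9 months | Stop at 12 months |
|---|---|---|---|
| 10% | 4.4% | 5.8% | 7.2% |
| 20% | 9.1% | 12.0% | 14.7% |
| 30% | 14.1% | 18.4% | 22.5% |

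The largest shortfall is 1 − 4.4/10 = 56%. The smallest is 1 − 22.5/30 = 25%.

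**Whole arm.** If a share f of the arm stopped early, the arm's crude figure is f × (crude risk if stopped) + (1 − f) × R. With R = 20% and f = 50% stopped at 6 months: 0.5 × 9.1 + 0.5 × 20 = 14.6%. With f = 10% stopped at 12 months: 0.1 × 14.7 + 0.9 × 20 = 19.5%. Both shares are assumptions.

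**Sensitivity to event timing (R = 10%).** If half of the cumulative hazard falls in the first 3 months and the rest is spread evenly, subjects who stop at 6 or 9 months show 6.8% or 7.6%. If all of it falls in the first 3 months, they show 10.0%, so there is no bias.

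**What a rate does.** Under a constant hazard, first events divided by person-time to first event recover the true rate (ratio 1.00) whatever share stops early. If all events fall in the first 3 months, events per total observed time overstate the stopped group by 20.96/8.96 = 2.34 times at a 6-month stop and 20.96/14.96 = 1.40 times at 12 months. Censoring at first event barely changes this at a 10% risk, since nine in ten subjects contribute all their time. A rate alone can therefore mislead in the other direction.

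**The case against.** The strongest reply is that shortened follow-up is not a stated fact. The SAP plans 18 months for every arm. What it states outright is that carriers were no longer randomised to 10 mg/kg biweekly, which changes the arm's case mix and not anyone's observation time. The revision table for version 4.0 describes the same matter as a lack of carriers, due to a change made midway through randomisation. The inference of early stopping rests on one phrase in an efficacy rationale. This objection stands as to certainty: the number of carriers stopped, and when, are unknown. It does not remove the concern, because section 5.4.4 lists the loss and the inability to randomise as separate items.

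A reader might go further and infer that time on drug is known to differ by arm, most of all in these carriers, so that the arm must look safer. The documents do not support that. They give no exposure by cell and nothing on the timing of AEs, and with early events the crude percentage is unbiased.

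It is also fair to say that the AE tables are descriptive, with no test or regimen decision attached, and that exposure duration and subject-months by arm let a reader notice unequal exposure. However, subject-months and percentages in separate tables do not yield a first-event rate. Sections 5.5.3 and 5.7 do not fill the gap: the first relates AEs to exposure to BAN2401 within the PK/PD analyses, and the second allows ad hoc work only.

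**Conclusion.** The point holds as a modest, inexpensive improvement. It is not an error or an internal contradiction. The SAP summarises TEAEs only as crude percentages while counting stops 90 days after last dose, and its own text gives reason to expect unequal observed time in one planned arm-by-APOE4 cell. Under the stated assumptions (constant hazard, stop at 6 to 12 months instead of 18, 90-day window in both groups, risks of 10% to 30%), the crude percentage is about 25% to 56% too low in the affected subjects. The effect is smaller for the whole arm and zero if all events come early. The direction is therefore possible, not assured, and its size cannot be settled from the SAP.

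**What to change.** In section 5.6.2, for special-interest TEAEs, SAEs and TEAEs leading to discontinuation, add beside the crude tables:

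1. cumulative incidence of the first event over time since first dose;
2. the rate of first events per person-time at risk, where time at risk is dosing time plus 90 days, censored at the first event.

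Give both by arm and by APOE4 status within arm. State that the rates are to be read with the cumulative-incidence curves, because the rate depends on the shape of the hazard, and that no comparison rests on the rate alone. Keep the crude percentages.

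The cost is SAP wording and a few more tables and figures from AE and dosing dates; no new data are needed. The change does not correct the shift in case mix from no longer randomising carriers to 10 mg/kg biweekly. The APOE4-stratified AE tables already planned address that.

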5.6.3 C-SSRS

The C-SSRS responses will be mapped to C-CASA. The incidence of Treatment Emergent suicidal ideation or suicidal behavior in treated subjects will be summarized by treatment group. Continuous variables will be summarized by descriptive statistics; number of subjects, mean, standard deviation, median, minimum, and maximum and categorical variables by number (percentage) of subjects. Subjects who already had suicidal ideation or behavior at baseline will be excluded from summaries.

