5.6 SAFETY ANALYSES

Evaluations of safety will be performed on the Safety Analysis Set. The incidence of AEs (including changes from baseline in physical examination), out-of-normal-range laboratory safety test variables, abnormal ECG findings, anti-BAN2401 antibody titers, and out-of-range vital signs, suicidality (C-SSRS), along with change from baseline in laboratory safety test variables, ECGs, safety MRI, and vital sign measurements, will be summarized by treatment group using descriptive statistics. The safety analysis will be also be summarized by the following safety subgroups: age (≤ 65 , $65 < \text{age} < 80$, ≥ 80 years), sex (male, female), race (white, black, Asian, other), region, *APOE4* status, and clinical subgroup (MCI due to AD – intermediate likelihood or mild Alzheimer’s disease dementia).

Study Day 1 for all safety analyses is defined as the date of the first dose of study drug.

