5.6.5 Laboratory Values

Laboratory results will be summarized using Système International (SI) units, as appropriate. For all quantitative parameters listed in [protocol Section 9.5.1.5 Safety Assessments \(Laboratory Measurements\)](#), the actual value and the change from baseline to each post-baseline visit and to the end of treatment (defined as the last on-treatment value) will be summarized by visit and treatment group using descriptive statistics. Qualitative parameters listed in [protocol Section 9.5.1.5](#) will be summarized using frequencies (number and percentage of subjects), and changes from baseline to each post-baseline visit and to end of treatment will be reported using shift tables. Percentages will be based on the number of subjects with both non-missing baseline and relevant post-baseline results.

Laboratory test results will be assigned a low/normal/high (LNH) classification according to whether the value was below (L), within (N), or above (H) the laboratory parameter's reference range. Within treatment comparisons for each laboratory parameter will be based on 3-by-3 shift table that compares the baseline LNH classification to the LNH classification at each post-baseline visit and at the end of treatment. Similar shift tables will be used to compare the baseline LNH classification to the LNH classification for the highest and lowest value during the treatment period.

The Sponsor's Grading for Laboratory Values (see [Appendix 13.1](#)) presents the criteria that will be used to identify subjects with treatment-emergent markedly abnormal laboratory values (TEMAV). Except for phosphate, a TEMAV is defined as a post-baseline value with an increase from baseline to a grade of 2 or higher. For phosphate, a TEMAV is defined as a post-baseline value with an increase from baseline to a grade of 3 or higher. When displaying the incidence of TEMAVs, each subject will be counted once in the laboratory parameter high and in the laboratory parameter low categories, as applicable.

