5.6.8 Other Safety Analyses

No other safety analyses are planned for this study.

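### The C-SSRS rule leaves out every subject with baseline ideation or behavior, so worsening from baseline appears in no C-SSRS summary

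*SAP*

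**What the plan says.** SAP Section 5.6.3 maps C-SSRS responses to C-CASA and states the outcome: "The incidence of Treatment Emergent suicidal ideation or suicidal behavior in treated subjects will be summarized by treatment group". Its last sentence sets the population: "Subjects who already had suicidal ideation or behavior at baseline will be excluded from summaries". The section does not define treatment-emergent for this scale. It plans no shift table, and it provides no count or separate display of the excluded subjects.

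The introduction to Section 5.6 says "Evaluations of safety will be performed on the Safety Analysis Set" and names suicidality (C-SSRS) among the items to be summarized. As Section 5.2.1 defines it, that set requires at least one dose and one post-dose safety assessment; baseline suicidality plays no part. Section 5.6.8 closes the safety part with "No other safety analyses are planned for this study".

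**The concern.** The outcome is described as covering treated subjects, but the last sentence narrows it to treated subjects with no baseline finding. The exclusion joins ideation and behavior with an *or*, so one baseline finding of either kind removes the subject for both. A subject with ideation only at baseline is thus lost even if the on-treatment event is a first suicidal behavior.

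A C-SSRS safety summary should show both new onset and escalation. Under the rule as written it shows new onset only. A reader of the six-arm table could not tell whether anyone with a baseline finding got worse, or how many such subjects each arm had.

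**Working it through.** No arithmetic figure in the SAP bears on this point: it gives no C-SSRS counts and no baseline prevalence. The check is a reading of the rule against cases, and then against the SAP's other safety rules.

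**Step 1. What the rule does with each kind of subject (Section 5.6.3).**

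| Baseline C-SSRS | On treatment | In a C-SSRS summary? |
|---|---|---|
| No finding | No finding | Yes, denominator |
| No finding | Ideation or behavior | Yes, numerator and denominator |
| Ideation only | More severe ideation | No |
| Ideation only | First behavior | No |
| Behavior | Further behavior | No |
| Any finding | Unchanged or improved | No |

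Every row with a baseline finding is absent, whatever happens later.

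**Step 2. What quantity results.** In one arm, let N be the treated subjects with data and b those with a baseline finding. Let e0 be the number with new-onset events among the N − b others, and e1 the number who worsen among the b.

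- The plan shows e0 / (N − b).
- A measure over all treated subjects would be (e0 + e1) / N. This is the weighted average of e0 / (N − b) and e1 / b, with weights (N − b)/N and b/N.
- The all-subject figure is therefore higher than the one shown only if e1 / b exceeds e0 / (N − b).

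The SAP gives none of b, e0 or e1, so neither the direction nor the size of the difference can be derived from it. What can be said is that e1 and b are not displayed.

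**Step 3. How the other safety rules treat a positive baseline.**

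- Adverse events (5.6.2): an event present before treatment counts if it came back, "Reemerged during treatment, having been present at pretreatment (Baseline) but stopped before treatment, or" or if it "Worsened in severity during treatment relative to the pretreatment state, when the AE was continuous".
- Anti-drug antibodies (5.6.4): a rise above a pre-existing titer counts as positive.
- Laboratory values (5.6.5): with phosphate treated separately, "a TEMAV is defined as a post-baseline value with an increase from baseline to a grade of 2 or higher". Shift tables start from the baseline class, including low and high.
- ECG (5.6.7): shifts are shown from each baseline class, both abnormal classes included.

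All four keep subjects whose baseline is abnormal or positive and can show change from it. The C-SSRS rule is the exception, and no reason is given.

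**Step 4. Is the loss recovered elsewhere in the SAP?** Section 5.6.8 plans nothing further. Section 5.6.2 recovers part of it: worsening or re-emergence reported as an adverse event enters the treatment-emergent tables, serious events have their own table, and "All AEs, treatment emergent or otherwise, will be presented in subject data listings". The SAP does not say that C-SSRS findings are recorded as adverse events, so this route depends on reporting rules outside the document.

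**The case against.** The strongest defense is that removing subjects with a baseline finding is a coherent way to define new-onset incidence. That stands for that one statistic. It does not explain why the exclusion covers the C-SSRS summaries in general, with no companion display of worsening.

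Three stronger readings are tempting, and the SAP does not support them:

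- A reader might infer that worsening in these subjects is counted nowhere. It can still reach the adverse event and serious adverse event tables and listings. The gap is in the C-SSRS summaries.
- A reader might infer that their worsening is scored as zero, so that incidence is understated. Excluded subjects leave both numerator and denominator, and Step 2 shows that the direction depends on rates the SAP does not give. Nor does the SAP call them the subjects at highest risk or give a number of them. Any eligibility limit on suicidality would be in the protocol, which is not at hand, so the number could be very small.
- A reader might infer a contradiction with the treatment-emergent definition in Section 5.6.2. That definition governs adverse events, and laboratory and antibody results also have their own. This is an inconsistent approach across domains, not two rules in conflict over the same data.

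It is also fair to say that the consequences are limited. The C-SSRS summary carries no test or stopping rule, an unblinded DSMB monitors safety (Section 3.2), and Section 11 leaves table and listing layouts to a separate document. None of this changes the population rule that Section 5.6.3 states.

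**Conclusion.** The point holds as a completeness gap. Followed as written, Section 5.6.3 shows no worsening from a baseline finding in any C-SSRS summary, including a first behavior after ideation only. That is out of line with the SAP's other safety rules and sits badly with the Safety Analysis Set named for the C-SSRS in Section 5.6. The number of subjects affected is unknown from the SAP, and no bias between arms is shown. The conclusion rests only on the text of the rule and on the absence of any other planned C-SSRS analysis. It needs no assumed prevalence. It is a modest point, worth correcting because the remedy is cheap.

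**What to change.** Make three changes to Section 5.6.3:

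1. Confine the exclusion of subjects with baseline ideation or behavior to the new-onset incidence, and report the number excluded in each arm.
2. Define treatment-emergent for the C-SSRS so that it includes worsening from baseline as well as new onset. First behavior after baseline ideation only should count as worsening.
3. Add a shift table from baseline category to worst post-baseline category, by treatment group, for all treated subjects with post-baseline C-SSRS data.

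The cost is SAP wording and one extra table from data already collected. Efficacy analyses and trial conduct are unaffected.
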